3.1. Overall Study Design and Plan

This is an open label safety and tolerability extension study for patients who have completed the TR03 study. Patients will either enter directly into a drug Treatment Period (Worst Itch NRS ≥ 5) or enter an extended screening period of a no-drug Observation Period (Worst Itch NRS < 5) based on their reported NRS scores on the first Visit (Visit 1a). For up to 12 extended screening weeks, patients in the no-drug Observation Period may also transition into the drug Treatment Period if their Worst Itch NRS increases to ≥ 5 .

To allow for various starting levels of pruritus intensity, patients who have a Worst Itch NRS that is ≥ 5 will enter the Treatment Period upon completion of Visit 1a. Patients whose Worst Itch NRS score is < 5 will be entered into an extended screening period, no-treatment criteria Observation Period for up to 12 weeks or until they develop a higher level of pruritus (i.e., Worst Itch NRS ≥ 5), at which point they will transition to the Treatment Period upon completion of Visit 1b. All patients entering the Treatment Period, whether immediately upon study entry or following a period of time in the Observation Period, will initially be titrated to a dose that can be as high as 180 mg twice daily (BID) during the first 4 weeks of the Treatment Period. Patients who continue in the Observation Period and maintain a Worst Itch NRS score of < 5 will be screen failed from the study at the end of the 12-week period. For enrolled patients whose Visit 1a worst itch NRS score satisfies the ≥ 5 enrollment criterion and for whom treatment is initiated, the screening visit Visit 1a will also be designated as the baseline visit. For enrolled patients who must continue into the Observation Period, the first visit during that period when the worst itch NRS ≥ 5 criterion is satisfied will be designated as Visit 1b and that visit will serve as the baseline visit.

The total study duration for any individual patient will be up to 53 weeks. For patients who enter directly into the Treatment Period, the total amount of time on drug will not exceed 50 weeks. Patients who enter the Treatment Period from the Observation Period, the total amount of time spent in the combined two periods of the study cannot exceed 50 weeks. All patients who received drug treatment will have a 2-week Washout and Safety Follow-up period at the end of the dosing period, unless consent is withdrawn.

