3.2. Premature Discontinuation of Study Drug Treatment

3.2.1. Premature Discontinuation of Study Drug Treatment Associated with Failure-to-Improve Criterion

Patients who meet failure-to-improve criterion during the conduct of the study, will stop taking study medication.

The Failure-to-Improve criteria are as follows: Beginning on Treatment Period Visit 3 (TV3), and at every subsequent Treatment visit, patients with a worst itch NRS score \geq the worst itch NRS score at Visit 1a (or at Visit 1b in the case of patients who require the OV period) will be discontinued from study drug. Patients discontinued from study drug are to undergo the End of Treatment Visit (TV14), the Washout/Safety Follow-up Period assessment in two weeks, and receive a follow-up telephone contact 30 days following end of study drug dosing for final safety assessment.

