4.6.2. Safety

The Safety population will consist of all enrolled patients who have received a single dose of study medication in the TR03 extension study. The Safety population will be used to evaluate the safety and efficacy endpoints defined for this study.

Patients will be summarized in a single nalbuphine treatment group.

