9.1. Adverse Events

Details regarding the definition and reporting of an AE or a serious adverse event (SAE) are provided in the study protocol. AEs will be recorded starting with the signing of the first

informed consent. All AEs will be collected through the Washout and Safety follow up visit (or Early Termination Visit). Following the Washout and Safety follow up visit (or Early Termination Visit), all unresolved AEs that were reported by the Investigator to be probably drug related should be followed by the Investigator until the events are resolved, the patient is lost to follow-up, or the AE has stabilized.

Non-serious AEs that begin during the Observation Period will be captured as medical history in the TR03 extension study; patients who never transition from the Observation Period to the Treatment Period are screening failures and did not complete the early termination or end of study CRFs. SAEs occurring during the Observation Period will be recorded as SAEs.

Also, AEs that were ongoing at the time of a patient's completion of the TR03 core study are recorded as medical history in the TR03 extension study.

A treatment-emergent AE (TEAE) will be defined as one starting or worsening on or after the first dose of study medication during the extension study. If the start date is missing, the event is assumed to be treatment emergent.

For patients who complete study treatment through the Visit 14/End of Treatment visit, Titration Period AEs are those with an onset date from first dose date of the extension study through (first dose date + 27 days). Treatment Period AEs are those with an onset date from first dose date of the extension study through (first dose date + 349 days). Washout and Safety Follow-up AEs are those with an extension study onset date of (first dose date + 350 days) through (first dose date + 363 days). For patients who are treated and who discontinue study drug use prior to the Visit 14/End of Treatment visit yet remain on-study, AEs with an onset date on or after the first dose date of the extension study will be considered Treatment Period AEs.

For the purpose of inclusion in TEAE table summaries, incomplete AE onset and end dates will be imputed as described below.

For incomplete AE onset dates:

- If the day is missing but the month and year are known:
 - If the month and year are different from the month and year of the first dose of study drug, then use the first day of the month as the imputed onset date.

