In all AE summary tables, TEAEs will be presented in descending order of incidence from the SOC with the highest total incidence to the SOC with the lowest total incidence. If the total incidence for any two or more SOC is equal then the SOC will be presented in alphabetical order. Within each SOC, the PTs will also be presented in descending order of total incidence among the active treatment arms with ties at the PT level being presented in alphabetical order. At each level of patient summarization, a patient is counted once if the patient reported one or more events. Percentages will be calculated out of the number of patients in the safety population.

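### AE percentages divide by all dosed patients in every period with no allowance for time at risk, so they can understate 50-week risk, and the Washout percentage is wrong as written

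*SAP*

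**What the plan says.** Section 9.1 fixes the denominator for all AE tables: "Percentages will be calculated out of the number of patients in the safety population". Sections 9.1.3, 9.1.6 and 9.1.7 repeat it for severity, special-interest and abuse-potential AEs. Section 4.6.2 defines that population by dosing alone: "The Safety population will consist of all enrolled patients who have received a single dose of study medication in the TR03 extension study".

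Sections 9.1.1, 9.1.3, 9.1.6 and 9.1.7 repeat the summaries for the Titration, Treatment and Washout periods. None of them gives a number at risk for the period. Section 9.1 sets the period limits by calendar offset from first dose, for patients who complete through Visit 14: Titration runs "through (first dose date + 27 days", Treatment "through (first dose date + 349 days", and Washout from "first dose date + 350 days) through (first dose date + 363 days". For patients who stop drug early but stay on study, every AE from first dose onward is assigned to the Treatment Period.

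Follow-up is unequal by design. Section 3.2.1 takes patients whose worst itch is no better than at baseline off drug: "Beginning on Treatment Period Visit 3 (TV3), and at every subsequent Treatment visit". Section 7.3.1 places Visit 3 at Week 5. For patients who enter through the Observation Period, which lasts up to 12 weeks, Section 3.1 says "the total amount of time spent in the combined two periods of the study cannot exceed 50 weeks".

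The primary endpoint (Section 3.3.1) is the incidence and nature of treatment-emergent AEs in treatment weeks 5-50. Exposure is summarised on its own in Section 7.3.2. Days to first onset and AE duration are planned only for special-interest and abuse-potential AEs.

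**The concern.** The primary objective is safety over up to 50 weeks, and the primary endpoint covers Weeks 5-50, which is when the stopping rule acts. A patient taken off drug at Week 5 adds a full unit to the denominator but only a few weeks in which an event can be recorded. The more patients stop early, the lower the crude percentage becomes relative to the risk over 50 weeks of treatment. Section 8.5 recognises this mechanism for rescue medication, where it warns that the summaries depend on how long patients stay in the study. Nothing comparable is said or done for AEs.

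The Washout table has a different and more definite fault. Section 3.1 gives every treated patient a two-week washout unless consent is withdrawn, but the rules in Section 9.1 prevent some of these patients from ever having a Washout AE. They remain in the denominator, and their off-drug events appear as on-treatment events. The plan screens for withdrawal effects (Sections 9.1.7 and 9.2.1), so this table needs a sound denominator.

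**Working it through.** The SAP states no AE rate, dropout rate or sample size, so there is no figure of its own to reproduce. The period lengths and the Washout problem follow from the text. The size of the understatement needs assumptions.

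**Period lengths (Section 9.1).** Titration: 27 + 1 = 28 days. Treatment: 349 + 1 = 350 days = 50 weeks. Washout: 363 - 350 + 1 = 14 days. Treatment is 350/14 = 25 times as long as Washout, on the same denominator. The shortest full course after observation is 50 - 12 = 38 weeks.

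**Understatement of 50-week risk.** Let P be the risk if everyone were followed on drug for 50 weeks, and D the share who stop by Week 50, with stopping unrelated to AEs. The relative understatement is 1 - crude/P.

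*Constant hazard, gradual stopping after Week 4.* Per week, h = -ln(1-P)/50 and g = -ln(1-D)/46. Then crude = 1 - exp(-4h) + exp(-4h) × h/(h+g) × [1 - exp(-46(h+g))]. For P = 30% and D = 30%: h = 0.00713, g = 0.00775, crude = 0.0281 + 0.9719 × 0.4792 × 0.4958 = 0.259. The understatement is 1 - 0.259/0.30 = 13.7%.

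*All stopping at Week 5.* Crude = (1-D)P + D[1 - exp(-5h)]. For P = 30% and D = 50%: 0.150 + 0.5 × 0.0350 = 0.1675, or 44.2% too low.

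*Events clustered early.* A share f of events falls in the first 4 weeks, and the rest have constant hazard with gradual stopping. For P = 50%, f = 70%, D = 30%: the early part is 0.35, the remaining conditional risk is 0.15/0.65 = 0.231, of which 0.196 is observed. Crude = 0.35 + 0.65 × 0.196 = 0.477, or 4.6% too low.

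| Assumed pattern | Share stopping | P | Relative understatement |
|---|---|---|---|
| 50-90% of events in first 4 weeks, gradual stopping | 30% | 10-80% | 2-8% |
| same | 50% | 10-80% | 3-14% |
| Constant hazard, gradual stopping | 20% | 5-80% | 7-9% |
| same | 30% | 5-80% | 10-15% |
| same | 50% | 5-80% | 19-25% |
| same | 80% | 5-80% | 35-46% |
| Constant hazard, all stop at Week 5 | 25% | 5-80% | 20-22% |
| same | 50% | 5-80% | 41-45% |
| Constant hazard, 40%, 20% and 10% stop at Weeks 5, 9 and 26, AEs counted for 2 more weeks | 70% | 20-60% | 49-53% |

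Counting AEs for two weeks after a gradual stop changes little: 9-13% instead of 10-15% at D = 30%, and 17-23% instead of 19-25% at D = 50%.

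**Titration.** The window closes at the end of Week 4 and the rule first acts at Week 5, so the rule removes nobody from it.

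**Washout.** A completer with k weeks of observation has at most 50 - k weeks on drug. The last dose is then no later than offset 349 - 7k days, and the two-week washout runs no later than offsets 350 - 7k to 363 - 7k.
- k = 0: 350 to 363, as the window assumes.
- k = 1: 343 to 356, so half the washout lies inside the window.
- k = 2: 336 to 349, so none does.
- k = 12: 266 to 279, so none does.

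Early stoppers who stay on study contribute none by the explicit rule. If washout risk is alike in all patients, the percentage is therefore too low by at least D (30% too low when 30% stop), and further by the share of completers with two or more weeks of observation.

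**The case against.** Four points can be made for the plan.

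- **The endpoint is descriptive.** No inference is planned, and the crude percentage is the share of treated patients with an AE under a regimen that includes the stopping rule. This stands. The percentage is biased only if read as the risk over 50 weeks of treatment, which is how a long-term safety figure is likely to be read.
- **Retention is visible elsewhere.** Disposition, failure-to-improve by visit, discontinuation by visit and exposure are all tabulated, and total event counts with mean exposure give a rough event rate. This stands in part. That rate would count repeat events and washout events in the numerator, while exposure ends at last dose, and it cannot be split by period. Days to onset describe only patients who had the event.
- **Early clustering can be seen.** Titration is tabulated as a subset of Treatment, and dose rises only in Weeks 1-4. This stands, and it shrinks the understatement to a few percent if most AEs occur then.
- **Patients who stop because of an AE are already in the numerator.** This also stands, and it makes the independence assumption a simplification.

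A reader might infer that 50-week incidence is understated by 20-50% and that every period column is affected. The SAP does not support that. It gives no dropout or AE rate. Under constant hazard with gradual stopping, roughly 40-55% of patients must stop to reach even 20%, and values near 50% need half or more to stop, mostly near Week 5. The rule does not touch Titration.

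**Conclusion.** The point holds in two parts.

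First, the AE percentages carry no allowance for time at risk, although exposure is unequal by design in the window of the primary endpoint. They remain correct as shares of treated patients, but they understate 50-week risk if AEs continue to arise after titration and stopping is unrelated to them. The relative size is assumption-based: about 2-8% if 30% stop and most AEs fall in titration, 7-15% if 20-30% stop gradually under constant hazard, and about 40-50% if half or more stop, mostly near Week 5. No single figure can be drawn from the SAP.

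Second, and without any assumption about rates, the Washout table is wrongly constructed. Its denominator includes patients who by definition cannot have an event in it, and their off-drug events are moved into the Treatment Period. Its size depends on the share of such patients.

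This should be changed before the tables are programmed. It does not invalidate the crude tables as descriptions.

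**What to change.** Keep the crude tables and amend Section 9.1 as follows.

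- For any treatment-emergent AE, serious AEs and special-interest AEs, add patients with a first event per 100 patient-years at risk, and cumulative incidence at Weeks 4, 26 and 50.
- Add a Weeks 5-50 summary, matching Section 3.3.1, among patients at risk at the start of Week 5.
- In the Treatment Period, count both time and events from first dose to actual last dose. This replaces the fixed 349-day limit and the rule that assigns all AEs of early stoppers to Treatment.
- Define Washout for every treated patient as the 14 days after the actual last dose. Time at risk runs to the first event or the end of AE collection, and the denominator is patients entering washout.
- Print the number of patients and the patient-time at risk for each period.
- State that ending time at risk at last dose assumes stopping is unrelated to the AE concerned.

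The cost is a little programming from dates already in the plan (first dose, last dose, AE onset, visits). The reported long-term incidence may look less favourable.

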9.1.1. Incidence of Adverse Events

An overview summary of the number and percentage of patients with any TEAE and the total number of TEAEs recorded will be presented for: patients experiencing any TEAE, any treatment-emergent SAE, any related TEAE, any TEAE by maximum intensity, and any TEAE by treatment period for the Treatment Period and Washout and Safety Follow-up Period.

The overview summary will be repeated for the Treatment Period and Washout and Safety Follow-up Period. For an AE that is reported during more than one of these periods, the earliest period of onset will be used in the incidence calculation. Additionally, the overview summary will be repeated for the Titration Period. Since the Titration Period is a subset of the Treatment Period, AEs will be reported in both periods, where applicable.

Summaries of the total number of TEAEs and the number and percentage of patients with at least one TEAE will be provided by SOC and PT.

A summary of the total number of AEs occurring during the Observation Period (captured in the TR03 extension study medical history form) and the number and percentage of patients with at least one AE during the Observation Period will be provided by body system and dictionary term. New medical history for the TR03 extension study (i.e. with an onset date on or after the signing of the informed consent for the TR03 extension study) is captured in the TR03 extension study medical history form.

All AEs will be presented in a data listing for the safety population.

9.1.2. Relationship of Adverse Events to Study Drug

Association or relatedness to the study medication will be graded as either “probably,” “possibly,” or “unlikely.” For the purpose of summarization, AEs will be dichotomized into “related” (probably and possibly) and “unrelated” (unlikely).

A summary of TEAEs by relationship (“related”, “unrelated”) to study drug will be presented in a table by incidence of occurrence. A patient with two or more AEs within the same level of summarization will be counted only once in that level using the most related category. TEAEs that are missing a relationship will be presented in the summary table as “related” but will be presented in the data listing with a missing relationship.

9.1.3. Severity of Adverse Events

The severity of all AEs will be graded by the investigator as Grade 1, Grade 2, Grade 3, Grade 4, or Grade 5 according to the [Common Terminology Criteria for Adverse Events \(CTCAE\) version 4.03](#).

A summary of TEAEs by severity will be presented. The severity that will be presented represents the most extreme severity captured on the eCRF page (Grade 1 through Grade 5 with Grade 5 being the most severe). A patient with two or more AEs within the same level of summarization will be counted only once in that level using the most severe incident. TEAEs that are missing severity will be presented in tables as “Severe” (i.e. Grade 3) but will be presented in the data listing with a missing severity. Percentages will be calculated out of the number of patients in the safety population.

The summary of TEAEs by severity will be repeated for the Treatment Period and Washout and Safety Follow-up Period. For an AE that is reported during more than one of these periods, the earliest period of onset will be used in the incidence calculation. Additionally, the summary will also be repeated for the Titration Period. Since the Titration Period is a subset of the Treatment Period, AEs will be reported in both periods, where applicable.

9.1.4. AEs Leading to Treatment Discontinuation

The incidence of AEs leading to study drug discontinuation will be summarized by SOC and PT and will be presented in a data listing. This listing will be a subset of the full listing of all AE information.

9.1.5. SAEs and Deaths

A summary of the total number of treatment-emergent SAEs and the number and percentage of patients with at least one treatment-emergent SAE will be provided by SOC and PT. An additional summary of all SAEs will be provided, broken down by the AE severity grade and investigator assessment of relationship to treatment. The summaries will also be presented separately for the Treatment Period and the Washout and Safety Follow-up Period.

A summary of the total number of SAEs during the Observation Period and the number and percentage of patients with at least one SAE during the Observation Period will be provided by SOC and PT. An additional summary of all SAEs during the Observation Period will be provided, broken down by the AE severity grade and investigator assessment of relationship to treatment.

All SAEs and fatal AEs will be presented in data listings for the safety population. These listings will be subsets of the full listing of all AE information.

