4.6. Analysis Populations

4.6.1. All Enrolled

An enrolled patient is one who provides consent to participate in the TR03ext study.

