8.6. Premature Discontinuation Due to Lack of Efficacy or Adverse Events

The distribution of patients who prematurely discontinue due to lack of efficacy or adverse events during the Treatment Period and Washout Period will be summarized for the safety population across all Treatment Period visits, separately at each Treatment Period visit, and for the Washout Period. Date of discontinuation during the Treatment Period will be defined as the date of last dose of study medication. For patients who complete the Treatment Period, date of discontinuation during the Washout Period will be defined as the earliest non-missing of the date of last contact or the last observed visit date.

9. Safety Analysis

All analyses of safety will be conducted using the safety population.

No formal statistical analysis will be performed on safety outcomes; inferences, if any, will be derived through clinical review and interpretation.

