 - If the month and year are the same as the month and year of the first dose of study drug, and the end date (after any imputation) is on or after the first dose of study drug, then use the date of the first dose of study drug as the imputed onset date.
 - If the month and year are the same as the month and year of the first dose of study drug, and the end date (after any imputation) is prior to the date of the first dose of study drug, then use the end date as the imputed onset date.
- If the month is missing but the year is known (day can be either missing or known):
 - If the year is different from the year of the first dose of study drug then use Jan. 1st of the reported year as the imputed onset date.

- If the year is the same as the year of the first dose of study drug and the end date (after any imputation) is on or after the first dose of study drug then use the date of the first dose of study drug as the imputed onset date.
- If the year is the same as the year of the first dose of study drug and the end date (after any imputation) is prior to the date of the first dose of study drug, then use the end date as the imputed onset date.
- If the start date is completely missing, the event is assumed to be treatment-emergent.

For incomplete AE end dates:

- If the day is missing but the month and year are known then use the last day of the month as the imputed end date.
- If the month is missing but the year is known (and the day is either missing or known) then use Dec. 31st of the year as the imputed end date.

Adverse events will be coded according to MedDRA (version to be delineated in the clinical study report).

All AE summary tables will present system organ class (SOC) and preferred term (PT), will include counts of patients, and will be based on TEAEs. SOC will be displayed in descending order of frequency overall and then alphabetically. PT will be displayed in descending order of frequency overall and then alphabetically within SOC. A patient with two or more AEs within the same level of summarization will be counted only once in that level using the most extreme incident. Percentages will be based on the number of patients in the safety population.

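### The AE, SAE and death listings cover dosed patients only, so an Observation-Period SAE or death in a never-dosed enrolled patient is in no listing; by the general rules the Observation-Period tables have the wrong population and denominator.

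*SAP*

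**What the plan says.** **Populations.** Section 4.6.1 defines enrolment by consent: "An enrolled patient is one who provides consent to participate in the TR03ext study". Section 4.6.2 requires a dose for the safety population: "The Safety population will consist of all enrolled patients who have received a single dose of study medication in the TR03 extension study".

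**Who is never dosed.** Under Section 3.1, patients with a Visit 1a Worst Itch NRS of 5 or more go straight to treatment. The others are observed off drug for up to 12 weeks and are screen failed if they never reach the threshold. Section 9.1 keeps non-serious Observation-Period AEs as medical history. For serious events it says: "SAEs occurring during the Observation Period will be recorded as SAEs".

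**General rules.** Section 9 opens with: "All analyses of safety will be conducted using the safety population". Section 9.1 bases all AE summary tables on TEAEs and adds: "Percentages will be based on the number of patients in the safety population". Section 4.1 takes percentages over the analysis population of interest. It makes all consenting patients the default for listings unless something else is specified.

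**Observation-Period outputs.** Section 9.1.1 plans an AE table in which "the number and percentage of patients with at least one AE during the Observation Period will be provided by body system and dictionary term". Section 9.1.5 plans an SAE table in which the "number and percentage of patients with at least one SAE during the Observation Period will be provided by SOC and PT". Neither sentence names a population or denominator.

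**Listings.** Section 9.1.1 limits the full AE listing to the safety population. Section 9.1.5 does the same for serious and fatal events, "All SAEs and fatal AEs will be presented in data listings for the safety population", and calls these listings subsets of the full one.

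**The concern.** Safety and tolerability are the primary objective. The SAP collects SAEs from patients who are never dosed and plans Observation-Period tables that include severity and relationship to treatment. The population rules then exclude some of those patients from the outputs meant to show them.

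Two things are at stake. A recorded SAE or death in an enrolled patient could be absent from every listing in the study report. The Observation-Period percentages would also not estimate a rate among the patients at risk, because their denominator includes patients who spent no time in that period.

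**Working it through.** The SAP states no rate or sample size for this point, so there is no figure to reproduce. The check is of definitions first, then denominators.

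**Listings**

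1. A patient who consents, enters observation and never reaches the threshold is enrolled (4.6.1), is not in the safety population (4.6.2), and can have a recorded SAE (9.1).
2. The Section 4.1 default would list that SAE, but it yields where another population is specified. Sections 9.1.1 and 9.1.5 specify one.
3. The restriction cannot be read loosely. Sections 5.2 and 5.3 name all enrolled patients where that is the population wanted for a listing.
4. No other output clearly recovers the event. The listing in Section 6.2.1 covers core-study TEAEs and non-serious Observation-Period AEs. Section 5.1 says reasons for screening failure in the Observation Period are not collected. Section 9.1 says these patients have no early termination or end-of-study forms.
5. A patient who dies during the Observation Period cannot later be dosed. Every Observation-Period death therefore falls outside the fatal-AE listing.

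**Tables**

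Let D be the number of direct entrants, O the number entering observation, and t the share of O later dosed. Assume every direct entrant is dosed. Let x₁ be the number of patients with an Observation-Period event among those later dosed, and x₀ the number among those never dosed.

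- Safety N = D + tO
- Percentage under the general rules = x₁/(D + tO) = (x₁/tO) × tO/(D + tO)
- Percentage among those at risk = (x₁ + x₀)/O
- Share of patients with events omitted = x₀/(x₁ + x₀)

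The factor tO/(D + tO) is below 1 whenever D > 0, so any direct entrant dilutes the percentage.

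*Illustration, all counts assumed:* 100 enrolled, O = 40, D = 60, t = 0.5, and an event rate of 10% in both halves of O. Then x₁ = 2 and x₀ = 2, and safety N = 60 + 20 = 80.

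- As planned: 2/80 = 2.5%
- Among those at risk: 4/40 = 10%
- Omitted: 2/4 = 50%

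*Range over assumed splits* (100 enrolled, true rate 10%, expected values):

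| O | t | Safety N | Dilution factor | Planned % | Omitted |
|---|---|---|---|---|---|
| 20 | 0.25 | 85 | 5/85 = 0.06 | 0.6 | 75% |
| 20 | 0.75 | 95 | 15/95 = 0.16 | 1.6 | 25% |
| 40 | 0.50 | 80 | 20/80 = 0.25 | 2.5 | 50% |
| 60 | 0.25 | 55 | 15/55 = 0.27 | 2.7 | 75% |
| 60 | 0.75 | 85 | 45/85 = 0.53 | 5.3 | 25% |

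**TEAE rule**

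Section 9.1 defines a TEAE as starting or worsening on or after the first extension dose. An event that occurs wholly in the Observation Period precedes that dose. Read literally, the TEAE-only rule would empty the Observation-Period tables that Sections 9.1.1 and 9.1.5 ask for.

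**The case against.** The listing restriction is explicit and hard to contest. The objections concern how far the rest can be pressed.

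- **The tables' own text does not name the safety population.** This stands. The link runs through Sections 4.1 and 9. The denominator sentence in Section 9.1 sits in a paragraph about TEAE tables, which pre-dose events do not fit. One may say the denominator is unspecified rather than deliberately wrong. But a programmer following the stated rules would use the safety population, because nothing exempts these tables.
- **A reader might infer that all events in never-dosed patients disappear.** The SAP does not support that. The Section 6.2.1 listing for Observation-Period patients covers non-serious events and states no safety-population limit, so the Section 4.1 default may keep them. The loss from listings is clear only for SAEs and deaths.
- **A reader might infer that the Observation Period is the study's only untreated reference.** The SAP gives it no such purpose. Entrants may have received nalbuphine in TR03 (Section 4.10 names 90 mg and 180 mg arms), the two-week washout is also off drug, and observed patients are selected for a Worst Itch NRS below 5. No comparison with treated time is planned.
- **The primary endpoint is untouched.** This stands. It concerns TEAEs in treatment weeks 5-50.
- **A reader might infer that such SAEs go unreported altogether.** That goes too far. Section 9.1 leaves reporting details to the protocol, which is not at hand. The gap shown is in the SAP's outputs.

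**Conclusion.** The point holds on the SAP's own text. It is firm for the listings: an SAE or death in an enrolled patient who is never dosed appears in no AE, SAE or fatal-AE listing. For the Observation-Period tables it holds by the general rules, which remove never-dosed patients from the numerator and put direct entrants in the denominator.

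The size cannot be known, because the SAP gives neither the share entering observation nor the share later dosed. The figures of 0.6% to 5.3% against 10% rest on assumed counts and an equal event rate in dosed and never-dosed Observation patients; they show direction only. It would be tempting to gauge the effect by dividing by the dosed Observation patients alone. That is not the at-risk group, since never-dosed entrants belong in both numerator and denominator.

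This is more than missing detail, because following the stated rules would omit recorded serious events and give diluted percentages. It affects pre-dose safety outputs and leaves the primary endpoint as it is.

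**What to change.** 1. In Section 9.1.5, present the SAE and fatal-AE listings for all enrolled patients. Because they are described as subsets of the full AE listing, widen that listing in Section 9.1.1 in the same way or reword the subset sentence.
2. In Sections 9.1.1 and 9.1.5, make all patients who entered the Observation Period, dosed or not, the population and denominator for the Observation-Period AE and SAE tables.
3. In Sections 9 and 9.1, exempt these tables from the safety-population and TEAE-only rules.

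The cost is SAP wording and one population flag. The SAEs are already recorded. For non-serious events, completeness in never-dosed patients is not established, since those patients have no early termination or end-of-study forms; note this as a limitation beside the AE table.
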